1. ABSTRACT

Atrial fibrillation (AF) is a common, morbid condition. Anticoagulation to prevent thromboembolic strokes is a foremost priority in AF but adherence is challenging for patients and lapses in anticoagulation are common. Chronic disease self-management (CDSM) is a recognized program to enhance self-efficacy and improve adherence, quality of life, and patient-centered health outcomes. Rural patients with AF experience increased vulnerability to adverse outcomes due to geographic and social isolation, poor health care access, and limited health literacy. Study team will conduct a single-center parallel group randomized clinical trial to test the efficacy of a relational agent to improve patient-centered care in AF delivered by smartphone. The Principal Investigator and study team have used the agent - a computer character that simulates face-toface conversation using voice, hand gesture and gaze cues to provide education, monitoring and problem-solving - to improve health behaviors and outcomes in individuals with limited computer and health literacy. Here, the team will expand its successful 30-day relational agent pilot to develop a novel CDSM program for AF. This study will combine the relational agent with the AliveCor Kardia smartphone heart rate and rhythm monitor. The team will implement a 4-month CDSM curriculum and assess its sustainability at 8 and 12 months. The trial randomizes 264 patients with AF who are receiving anticoagulation for stroke prevention to (1) the relational agent and Kardia intervention, accompanied by provider alerts for prespecified results; or (2) the control, consisting of an AF educational session and a smartphone with a general health application (WebMD). Our aims are: (1) To assess the effect of the relational agent and Kardia intervention on anticoagulant adherence, as determined by the proportion of days covered (PDC), and selfreport. (2) To identify the effect of the intervention on health care utilization, hospitalizations, emergency visits, and AF-related procedures at 1-year follow up. (3) To determine the effect of the intervention on the patient-centered outcomes of quality of life and symptoms, as measured by the AF Effect on QualiTy of life (AFEQT) measure, specific to AF, and the general Patient-Reported Outcomes Measurement Information System-29 Profile at baseline, 4, 8 and 12 months. (4) To examine mechanisms for the effect of the intervention by symptom burden, AF classification, health literacy and intervention use. The trial will additionally follow the cohort through the study period for exploratory analyses of rurality and outcomes associated with AF. Expected Results: In this project we will evaluate a scalable patient-centered intervention to improve anticoagulation adherence, health care utilization and patient-centered outcomes in vulnerable rural individuals with chronic AF. If proven successful, this intervention can be broadly disseminated to improve the care of patients with AF.

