Statistical approach for Aim 3. We estimate that patients randomized to our intervention will have a clinically relevant improvement in HRQoL as demonstrated by AFEQT global score at 4-months follow-up vs. control. Our demonstration cohort (N=31) had a mean increase in AFEQT global score of 12±16 (from 64±23 to 76±19) over 30 days (range 0-100, greater scores indicating superior HRQoL). We will use linear regression adjusted for trial stratification factors and the baseline score as per Harrell⁴¹ to evaluate the differences in AFEQT global and domain-specific scores between study arms at 4 months. We will similarly assess the effect of the intervention for

each of the 4 AFEQT domains and the 8 symptom and HRQoL domains measured by the PROMIS-29 at 4 months. Next, we will assess sustainability of the intervention effect at 8 and 12 months using linear mixed models. Our power calculations assume a 90% 4-month assessment completion rate (to accommodate for 10% attrition), 2-tailed α =0.05, and standard deviation of 17 (representing the upper limit of the 95% confidence interval for the SD and consistent with the data used to determine the minimum important difference⁴²). Based on these assumptions, we expect our sample size (119 per arm) will enable us to detect a minimum difference in AFEQT between the two study arms at 4 months of at least 6.3, corresponding to 0.37 SD, a small effect size.³⁹ A 20% sample size attrition (n=106 per arm) at 12 months will allow us to detect a difference in AFEQT of at least 0.41 SD.

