Statistical approach for Aim 4. Subgroup analyses will be performed to assess moderation of the intervention effect by baseline patient-centered factors: (1) sex; (2) race (white vs non-white); (2) health literacy, assessed using the Newest Vital Sign (NVS); (3) AF classification (paroxysmal vs permanent), (4) symptom burden, measured by the AFEQT; (5) anticoagulant type (warfarin or direct oral anticoagulant (**DOAC**)); (6) self-reported anticoagulant nonadherence (<2 or \geq 2); and (7) duration of anticoagulation (<1 or \geq 1 year). We will formally test for effect modification by creating a regression model for each outcome including the subgroup variable, the intervention assignment and the interaction between the subgroup variable and intervention and evaluating the significance of the interaction term. The false discovery rate⁴³ will be used to adjust for multiple comparisons. Causal mediation analyses will be used to determine the degree to which intermediate patient-level factors explain the intervention effect as potential mediators of the primary and secondary outcomes.⁴⁴⁻⁴⁶ We will estimate the direct and indirect effects of the intervention on outcomes accounting for (1) changes in symptom burden during follow-up, measured by the AFEQT: (2) introduction of new AF therapies over 12-month study participation (antiarrhythmic, cardioversion or electrophysiologic study); (3) relational agent and Kardia usage; and (4) EHR alerts. Instead of emphasizing p-values, we will focus on estimation of mediation effect sizes.

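### The Aim 4 effect-modification models do not carry over the baseline score that Aim 3 uses for AFEQT and PROMIS-29, which costs the interaction tests precision

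*Combined protocol and SAP*

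**What the plan says.** All references are to the combined protocol and SAP.

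- **Section 5.0, Aim 4.** Effect modification is tested by "creating a regression model for each outcome including the subgroup variable, the intervention assignment and the interaction between the subgroup variable and intervention", and the significance of the interaction term is judged with false discovery rate control. Eight baseline moderators are listed: sex, race, health literacy, AF classification, symptom burden, anticoagulant type, self-reported nonadherence and duration of anticoagulation. One of them is "symptom burden, measured by the AFEQT". No adjustment covariate is named, and the paragraph does not refer back to the models of Aims 1 to 3.
- **Section 5.0, Aim 3.** For AFEQT at 4 months: "We will use linear regression adjusted for trial stratification factors and the baseline score". The same approach is extended to "each of the 4 AFEQT domains and the 8 symptom and HRQoL domains measured by the PROMIS-29 at 4 months". Sustained effects at 8 and 12 months are assessed with linear mixed models; how baseline enters those is not stated.
- **Section 8.1, Table 1.** AFEQT and PROMIS-29 are both collected at baseline and at 4, 8 and 12 months.
- **Pilot data, Section 5.0, Aim 3.** The demonstration cohort of 31 "had a mean increase in AFEQT global score of 12±16 (from 64±23 to 76±19) over 30 days".

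**The concern.** The same outcome is modelled in two ways. Aim 3 adjusts for the baseline score. Aim 4, as written, does not, except where the moderator is itself baseline AFEQT. For a quality-of-life score the baseline value is usually a strong predictor of the follow-up value, and here it is already on file. Interaction tests have much less power than main-effect tests on the same sample, so unexplained variance is most costly there. Without the baseline score, subgroup estimates also carry any chance baseline imbalance between arms, which tends to be larger in small subgroups. Moderation is part of a named aim (Section 3.4), and the race and sex analyses are meant to inform later studies. A null interaction from a needlessly noisy model would be a poor guide for them.

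**Working it through.** **1. The plan's nearest figure.** No power or residual variance is given for the Aim 4 tests. The closest figure is the Aim 3 detectable difference of 6.3 points (0.37 SD) with 119 per arm and "2-tailed α =0.05, and standard deviation of 17". Aim 3 states no power level; 85% is used for Aims 1 and 2.

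- Detectable difference = (1.960 + 1.036) × 17 × √(2/119) = 6.60 points (0.39 SD), not 6.3.
- With 132 per arm it is 0.369 SD = 6.27 points, which matches the stated figure.
- The companion 0.41 SD at 106 per arm reproduces at 85% power (0.412).

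So 6.3 appears to belong to the full sample before attrition. Nothing below depends on this.

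**2. Correlation implied by the pilot.** Inputs: baseline SD 23, follow-up SD 19, SD of change 16, N = 31.

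- r = (23² + 19² − 16²)/(2 × 23 × 19) = 634/874 = 0.725, so r² = 0.526.
- Fisher 95% CI for r: 0.50 to 0.86.

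**3. Cost in residual variance.** With baseline in the model, residual variance = 19² × (1 − 0.526) = 171 (SD 13.1). Without it, the variance is 361 (SD 19). Ratio = 1/(1 − 0.526) = 2.11; the standard error ratio is √2.11 = 1.45.

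| Assumed r | Variance ratio |
|---|---|
| 0.50 (lower 95% limit) | 1.33 |
| 0.60 | 1.56 |
| 0.725 (pilot) | 2.11 |
| 0.86 (upper 95% limit) | 3.81 |

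Rounding of the published SDs alone gives 1.92 to 2.33. In 1,500 simulated trials of 238 participants, fitted with and without baseline, the mean ratio was 2.11.

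**4. Cost in detectable interaction.** Assumptions: 119 per arm, a fraction p in the subgroup, two-sided 0.05, 85% power, no false discovery rate adjustment. SE = SD × √(2/(119p) + 2/(119(1 − p))); detectable interaction = 2.996 × SE.

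| Case | Without baseline | With baseline |
|---|---|---|
| p = 0.5, SD 19, r = 0.725 | SE 4.93; 14.8 points | SE 3.39; 10.2 points |
| p = 0.5, SD 19, r = 0.5 | 14.8 points | 12.8 points |
| p = 0.5, plan's SD of 17 taken as raw SD, r = 0.725 | 13.2 points | 9.1 points |
| p = 0.3 (planned non-white share), SD 19, r = 0.725 | 16.1 points | 11.1 points |

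For an illustrative 10-point interaction with p = 0.5 and SD 19, power is 53% without baseline, 84% with it at r = 0.725, and 65% with it at r = 0.5.

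**5. The symptom-burden moderator.** When the outcome and the moderator are both the AFEQT global score, a continuous moderator already supplies the baseline score, so there is no excess variance. A median split would leave a ratio of about 1.40, that is (1 − 0.335)/(1 − 0.526), because under normality it captures 2/π of r².

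**6. PROMIS-29 and the AFEQT domains.** No SDs or correlations are given. Over an assumed r of 0.4 to 0.8 the ratio runs from 1.19 to 2.78. This is a range of assumptions, not an estimate.

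**The case against.** **The sentence may not be a full specification.** It covers every outcome at once, including binary PDC and event counts, names no link function or time point, and uses a word (including) that does not shut out other terms. It could be read as listing what is added to the models already described. That reading is possible, so a reader should not infer that the plan forbids baseline adjustment. But Aims 1 to 3 each name their adjustment terms and Aim 4 names none, so an analyst following the text would fit three terms.

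**The factor of two is fragile and narrow.** This stands. It comes from 31 people in one cohort over 30 days, while the trial's outcomes are at 4 to 12 months, where the correlation may be lower. A reader might extend the doubling to PROMIS-29 or the AFEQT domains; the documents contain nothing to support that.

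**The gain does not rescue the tests.** Largely true. For an interaction as small as 6.3 points (evenly split subgroup, SD 19), power is about 25% without baseline and 46% with it. If only one of the eight moderators were real, an assumed threshold near 0.05/8 would cut the 84% above to about 59%. Better precision still helps at any threshold.

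**The Aim 3 and Aim 4 results do not conflict by design.** A reader might infer that subgroup effects cannot average to the main effect, or that they are biased. Neither follows. Under randomisation both linear models target the same effect and differ only by chance. Exact averaging is not guaranteed after the fix either, since the Aim 3 model has no subgroup term.

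**Conclusion.** The point holds as a loss of precision in the moderation tests of secondary outcomes. As written, the Aim 4 models omit the baseline score and the stratification factor that Aim 3 uses for the same outcomes. For AFEQT global the best available estimate is a 2.1-fold residual variance, with a plausible range of 1.3 to 3.8. That takes the detectable interaction in an evenly split subgroup from 10.2 to 14.8 points (9.1 to 13.2 if the raw SD is 17). These figures assume that the pilot correlation carries over to the trial's time points, 85% power and no multiplicity adjustment. Even at r = 0.5, adjustment is worth about a third more participants (1/0.75 = 1.33). The size for PROMIS-29 and the AFEQT domains is unknown. The interaction tests remain valid, and neither the primary PDC analysis nor the Aim 3 main effects are touched.

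**What to change.** Add to the Aim 4 paragraph of Section 5.0 that effect-modification models for AFEQT and PROMIS-29 outcomes are the corresponding Aim 3 model, with the baseline value of the score being analysed and the stratification factor, plus the subgroup variable and the arm-by-subgroup interaction. Three details complete it:

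- Where the moderator is itself the baseline AFEQT score being analysed and is kept continuous, enter that score once. State whether symptom burden is continuous or cut.
- Where the moderator is anticoagulant type, it is also the stratification factor, so it too enters once.
- For the 8- and 12-month mixed models, handle baseline as in the Aim 3 mixed model, and state there how that is done.

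The cost is a few lines of analysis-plan text, best added before any unblinded analysis. No new data or visits are needed, because both instruments are already scheduled at baseline.

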5.0 STATISTICAL CONSIDERATIONS

We propose a two-arm RCT to evaluate the efficacy of the relational agent and AliveCor Kardia heart rhythm monitor to improve patient-centered outcomes in patients with the debilitating chronic condition atrial fibrillation (AF). We will recruit 264 patients with AF receiving anticoagulation over a 30-month period, prioritizing recruitment in socioeconomically depressed regions in rural Northwest Pennsylvania. We will randomize participants 1:1 to receive the mobile relational agent and Kardia (n=132) or control (n=132) for 4 months, conducting randomization with a web-based data management system that we have used in prior RCTs. Randomization will be stratified by type of oral anticoagulant (warfarin or direct acting oral anticoagulant). We will assess the impact of our intervention at 4, 8 months and then at 12 months to determine sustainability. Our primary hypothesis will test whether the relational agent and Kardia intervention can improve adherence to anticoagulation as quantified by the PDC and by participant self- report. Our secondary hypotheses will evaluate 1) assessments of health care utilization between the intervention and control; 2) the improvement in health-related quality of life at 4, 8, and 12 months compared to the control, as measured by instruments specific to AF and general, validated quality of life assessments; and 3) the mechanisms for the effect of the intervention, as evaluated by assessments of moderation and mediation. All participants will have return visits at 4, 8, and 12 months. The outcomes will all be calculated without reference to intervention arm. We will use the intention-to-treat principle for all primary and secondary analysis. All analyses will be blinded to trial randomization arm.

Statistical approach for Aim 1. The primary outcome for Aim 1 is anticoagulant adherence as assessed by PDC. We will use the intention-to-treat principle for all primary and secondary

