analyses. We will analyze PDC as continuous (range 0-1, higher ratio indicating better adherence) and binary (optimally adherent if ≥0.8) variables. We will assess differences between the 2 study arms in PDC at 12 months with linear regression (for continuous PDC) or logistic regression (for binary PDC) adjusting for trial stratification factor (as suggested by Kahan and Morris³⁷). We will conduct our secondary assessments of adherence at 4 8, and 12 months similarly. We will categorize individuals scoring ≥ 2 on any of the 3 self-report adherence items (range 1-5, Voils et al.³⁸) as nonadherent. To assess whether the effect of the intervention changes over time, we will use linear (for continuous measures) or non-linear (for categorical measures) mixed-effect models with random intercepts with adherence measures modeled as a function of study arm, study visit and their interaction. We calculated the statistical power to detect a range of difference in PDC (our primary outcome) between the intervention and control arms. After accounting for 10% attrition through 12 months (consistent with our prior RCTs), we determined that a sample size of 119 in each study arm will enable us to detect a minimum difference in PDC between the two groups as small as 11.7% with 85% power (assuming a SD=30%). Our power calculations assume use of 2-sided tests with 0.05 significance level. With an additional, unexpected 10% attrition (n=106 per arm, to accommodate for relocation, loss-to- follow-up, institutionalization, or death), we will be able to detect a minimum difference in PDC as small as 12.4% (0.41 standardized mean difference) with 85% power. Both are considered small effect sizes per Cohen's guidelines.³⁹

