Statistical approach for Aim 2. We will compare HCU across trial arms in models that again account for trial stratification factor.³⁷ We will use the electronic health record (EHR) in concert with 4-, 8-, and 12-month self-report to catalog events (hospitalization, emergency room and ambulatory visits, medications, and procedures) and classify them as related to AF. We will determine person-year of follow-up as starting from the date of randomization to the 12-month visit. We will then classify HCU in aggregate and by item as count outcomes. We will use generalized estimating equations (GEE) negative binomial regression models (chosen instead of Poisson regression due to expected over-dispersion in the data). Similar approaches will be used to assess counts for each HCU component. Based on preliminary data from an outpatient registry of individuals with chronic AF, we expect there will be 42.0 events for every 100 person-years in the control arm of the trial.⁴⁰We estimate that we have 85% power to detect a minimum absolute reduction of 21 events per 100 person-years in the intervention group, assuming an equivalent number of events in the control group at 12 months with a sample size of 132 per arm. A 20% attrition in study participation (n=106 per arm) at 12 months will still allow us to detect a minimum of absolute reduction of 23 events per 100 person-years in the intervention group with 85% statistical power. As exploratory analyses, we will perform survival analyses to compare the time to event between the intervention and control arms for preselected outcomes: AF-related hospitalization, emergency visit, or procedure; myocardial infarction; heart failure; stroke; and allcause mortality. Participants will contribute 18 to 51 months of follow-up: those without the event of interest will be censored at the end of follow-up. We will examine the assumption of proportional hazards and use Cox regression models to estimate the hazards ratio for assigned treatment for each outcome.

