7.5 Randomization

Participants meeting all of the inclusion and none of the exclusion criteria will be randomized to one of 2 groups, a control and an intervention group. To ensure flexibility in achieving the proposed allocation of patients between study arms, permuted block randomization will be used. Additionally, randomization will be stratified by type of anticoagulant, (warfarin or DOAC) as DOACs do not require monitoring and are associated with fewer major bleeding events compared to warfarin.

If the participant is randomized to the treatment group, he or she will receive the ECA+Kardia app/hardware that will come pre-loaded onto a study iPhone that will be returned at the end of

the study. These study iPhones will either be mailed or provided to the participant in person.

Participants randomized to control will receive an educational session (over the phone or in person) and a brochure published by the American Heart Association that describes AF and the relevance of anticoagulation. Control participants will receive an Apple smartphone (identical to that received by intervention participants) with the WebMD (www.webmd.com/mobile) application installed and directions for its use. The WebMD app provides general health content and can be used for enhanced self-care. We will inform control participants that they may use the WebMD app to track symptoms and record and learn about their medications for AF and other conditions.

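### The written terms of the Aim 1 mixed model and Aim 4 moderator models omit the anticoagulant stratum and baseline outcome values: a minor loss of precision, free to repair

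*Combined protocol and SAP*

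**What the plan says.** All of the following is in section 5.0 of the combined protocol and SAP unless noted.

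- **Design.** "Randomization will be stratified by type of oral anticoagulant", with two levels, warfarin and DOAC. Section 7.5 adds that "permuted block randomization will be used".
- **Models that carry the stratum.** The 12-month PDC regressions are described as "adjusting for trial stratification factor", citing a paper on improper analysis of trials randomised in stratified blocks. Aim 2 opens by applying the same adjustment to the utilisation models. The 4-month AFEQT regression in Aim 3 adjusts for the stratum and for the baseline score.
- **Models whose terms are listed without it.** The Aim 1 longitudinal model has "adherence measures modeled as a function of study arm, study visit and their interaction", with random intercepts. The Aim 4 moderator models, one per outcome, are specified as "including the subgroup variable, the intervention assignment and the interaction between the subgroup variable and intervention".
- **Models with no covariates stated.** Aim 3 says only that linear mixed models will assess sustainability at 8 and 12 months. For the exploratory time-to-event outcomes, Aim 2 says the team will "use Cox regression models to estimate the hazards ratio for assigned treatment for each outcome".

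No general sentence extends the stratum or baseline adjustment to every model.

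**The concern.** When allocation is balanced within a prognostic stratum, the estimated arm difference no longer varies with stratum imbalance. A model that leaves the stratum out still counts the between-stratum spread as noise. Its standard error is then too large, its interval too wide, and its test below nominal size. The plan accepts this principle for its main models and then lists terms for two later sets of models that do not follow it.

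A baseline score is a separate matter of precision. Aim 3 uses it for 4-month AFEQT, whereas the Aim 4 models for the same outcome do not list it. Interaction tests in a trial of this size are weak to begin with, and section 5.0 says the trial was not designed to assess variation in effect by race or sex, so avoidable residual variance matters there.

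**Working it through.** **The plan's own figure.** With 119 per arm, SD 30, two-sided 0.05 and 85% power, the detectable PDC difference is (1.960 + 1.036) × 30 × √(2/119) = 11.65, or 11.70 with the t distribution. The plan states 11.7, so its figure reproduces. SD 30 is used below.

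**Stratum, arm contrasts.** The documents give neither the warfarin share p nor the PDC gap D between strata, so both are assumed. The share of variance due to the stratum is f = p(1−p)D²/30². Leaving it out inflates the SE by 1/√(1−f), and the true test size is 2[1 − Φ(1.96/√(1−f))].

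| p | D (points) | f | SE excess | True size |
|---|---|---|---|---|
| 0.3 | 10 | 0.21×100/900 = 0.023 | 1.2% | 4.7% |
| 0.3 | 20 | 0.21×400/900 = 0.093 | 5.0% | 4.0% |

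At D = 20 the SE excess is 2.1% if p = 0.1 (f = 0.09×400/900 = 0.040) and 6.1% if p = 0.5 (f = 0.25×400/900 = 0.111).

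In power terms, take a linear arm comparison at 119 per arm and an 11.7-point difference. The true SE is 30√(1−f)√(2/119), and the SE reported without the stratum is 30√(2/119).

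| Assumed f | Size without stratum | Power without | Power with |
|---|---|---|---|
| 1% | 0.049 | 85.4% | 85.6% |
| 5% | 0.044 | 85.9% | 87.0% |
| 10% | 0.039 | 86.5% | 88.7% |

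**Stratum, interaction tests.**

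- *Arm × subgroup.* In 10,000 simulated trials per setting (n = 238, 30% warfarin, blocks of 4, f = 1%, 5%, 10%), the size at nominal 0.05 was 0.048, 0.050 and 0.049 without the stratum, and 0.048, 0.051 and 0.049 with it. The test is valid either way, because allocation is not balanced on the stratum within subgroups. Adding the stratum can still reduce residual variance, but only by the factor 1−f, so the SE gain is bounded by the same 1% to 5%.
- *Arm × visit.* The stratum does not change over time and largely cancels from within-person change. In a small simulation (40 runs per setting, three visits, intraclass correlation 0.5), the ratio of SEs without and with the stratum was 1.000 with complete data. With 10% of visits missing at random it was 1.0002 for a 10-point gap and 1.0016 for a 20-point gap.

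**Baseline score, moderator models.** Aim 3 reports pilot AFEQT SDs of 23 at baseline, 19 at 30 days and 16 for change (N = 31). The implied correlation is r = (23² + 19² − 16²)/(2×23×19) = 634/874 = 0.725. Adjusting for baseline multiplies residual variance by 1 − r², and this carries through to the interaction coefficient.

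- r = 0.725: 1/√(1 − 0.526) = 1.45, an SE about 45% larger without baseline.
- r = 0.5 (assumed, for a longer interval): 1/√0.75 = 1.15, about 15% larger.

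**The case against.** The main comparisons (12-month PDC, utilisation counts, 4-month AFEQT) already carry the stratum. What remains is secondary or exploratory, and the error is conservative, so there is no added false-positive risk. All of this stands.

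The models with listed terms exist chiefly to test interactions. A reader might infer that leaving out the stratum undermines the change-over-time and moderation conclusions. The documents do not support that: the test sizes of 4.7% and 4.0% belong to arm main-effect or per-visit contrasts, and the interaction tests keep their size.

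A reader might also infer that the Cox and Aim 3 mixed models exclude the stratum by design. They do not. The Cox sentence names what is to be estimated, and the Aim 3 sentence names only a model class, directly after a regression adjusted for stratum and baseline. Aim 2's opening sentence could be read to cover the AF-related utilisation endpoint among the Cox outcomes, though not infarction, heart failure, stroke or death. For these models the gap is silence.

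The baseline argument has limits too. The Aim 4 wording need not be exhaustive. The symptom-burden and baseline-nonadherence moderator models already contain those baseline measures in some form. In the Aim 1 mixed model, self-reported adherence is collected at baseline (Table 1), so a baseline visit may already be intended as a repeated outcome. The 45% figure should therefore not be applied to the mixed models.

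**Conclusion.** The point holds as a minor, cost-free improvement. The written terms of the Aim 1 mixed model and the Aim 4 moderator models include neither the stratum (apart from the anticoagulant-type moderator model) nor a baseline outcome value, and the Aim 3 mixed and Cox models leave covariates open. The stratum effect is small and rests on an assumed warfarin share and stratum gap. The linear-model figures do not transfer exactly to the non-linear mixed or Cox models, where adjusted and unadjusted odds or hazard ratios are also different quantities.

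The baseline effect on the moderator models for AFEQT is potentially larger. The 45% is an upper figure, from 31 single-arm patients over 30 days; at 4 to 12 months the correlation, and so the loss, is probably lower. The documents give no correlation for PROMIS-29 or self-reported adherence. Nothing here touches the validity of the primary PDC comparison.

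**What to change.** Add to section 5.0 a statement that:

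- all arm-comparison, mixed and moderator models include the anticoagulant stratum, with the Cox models stratified by or adjusted for it;
- models for AFEQT, PROMIS-29 and self-reported adherence also include the baseline value, either as a covariate or, in the mixed models, as a baseline visit, saying which.

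No baseline term is added for PDC, because Table 1 schedules PDC only at 12 months. The cost is one or two sentences: the stratum is known at randomisation, and Table 1 already collects the three baseline measures. Sample size and data collection do not change.
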